Added that if subjects have non-MRI compatible devices fitted during treatment, then a computed tomography scan may be utilized to assess safety, if deemed appropriate by the investigator	To clarify that subjects would not need to withdraw from study	Synopsis 
 • Study Design Section 9.1.2.1 Section 9.5.1.5.7
Added that CSF will be used to assess PD, PK, and exploratory biomarkers.	Clarification	Synopsis 
 • Study Design Section 9.1.2.1
Added that CSF and PET assessments should be conducted before any other visit assessments and while the study is still study drug	Clarification	Synopsis 
 • Study Design Section 9.1.2 Section 9.1.2.1
Added that new AEs will be collected for 4 weeks post last dose and followed-up for 12 weeks, or until resolution, whichever comes first. AEs relating to study procedures will be collected until the end of study participation	Clarification	Synopsis 
 • Study Design Section 9.3.3
Historical cerebrospinal fluid (CSF) samples, if collected, processed, and stored under appropriate conditions and approved by the sponsor, may be analyzed to determine CSF amyloid positivity	Allows historical CSF sample to be analyzed to determine eligibility	Synopsis 
 • Inclusion Criteria • Assessments Section 9.3.1

Revisions to Version 6.0

New version/date: Version 7.0/21 Jan 2019 (per Amendment 06)

Change	Rationale	Affected Protocol Sections
Added that levels of Vitamin B12 may be confirmed with reflex testing to include methylmalonic acid analysis, if available in region	For flexibility on Vitamin B12 deficiency analysis	Synopsis 
 Exclusion Criteria Section 9.3.2 Table 3 Section 9.5.2.2 Table 6
Revised exclusion criterion (#14) regarding a prolonged QTc interval calculated using Fridericia's formula (QTcF) was changed to clarify that if the QTcF machine read is greater than 440 ms on the first single 12-lead ECG, 2 additional 12-lead ECGs will be performed.	Machine read QTcF values might be lower than central reads. Subjects are SF if the average of 3 ECGs on central read > 450 ms. Instructing sites to perform triplicate ECGs when machine reads are > 440 ms will ensure all required evaluations are completed.	Synopsis 
 Exclusion Criteria Section 9.3.2 Section 9.5.1.5.6 Table 5

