Eligible subjects may enter the Extension Phase immediately following the completion of Visit 15 of the Core Study. Subjects who are eligible to participate in the Extension Phase but who do not transition to the Extension Phase on the day of Visit 15 may enter the Extension Phase any time within 4 weeks of Visit 15. All subjects who enter the Extension Phase will be treated with elenbecestat, including the subjects who received placebo during the Core Study. For all subjects, assessments performed at Visit 15 will serve as baseline values for the Extension Phase.

During the Extension Phase, the assessment of safety will include the recording of all AEs. In addition, vital signs, weight, safety blood and urine laboratory tests, ECGs [no central reading of ECGs], suicidality, neurological examination, NPI, and signals of abuse potential will continue to be assessed.

A full neurologic examination will be performed at the start of the Extension Phase (during Visit 15, the last visit of the Core Study) and at Visit 24/ED, but will be abbreviated for all other timepoints.

Clinical assessments will be performed every 4 months (MMSE, FAQ) or 12 months (CDR, ADAS-cog14). Blood biomarkers and MRI will be assessed every 12 months. Optional amyloid and tau PET and CSF biomarker assessments will be conducted at the end of 2-year open-label treatment (Extension Phase).

Subjects who complete treatment in the Extension Phase or who discontinue the study drug are required to complete the Follow-up Visit, 1 month after the last dose.

Subjects may discontinue from the open-label study drug for any reason, but will be required to complete the ED Visit (within 7 days of last dose) and the Follow-up Visit 1 month after the last dose of study drug. In addition, subjects are required to discontinue the open-label study drug if any of the criteria specified in [Section 9.3.3](#), are met. (revised per Amendment 06)

Number of Subjects

The pooled data from 2 studies (E2609-G000-301 and E2609-G000-302) will comprise the total sample size of approximately 1900 subjects; at least 850 subjects will be randomized in each study. (revised per Amendment 06)

Inclusion Criteria

Subjects must meet all of the following criteria to be included in this study:

Core Study

1. MCI due to AD or mild AD disease according to the National Institute of Aging – Alzheimer’s Association (NIA-AA) core clinical criteria and must have all of the following at Screening: (revised per Amendment 04)

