Amyloid PET imaging or CSF AD assessment (eg, tau:A β (1-42) ratio) or both will be used to confirm that all study subjects have amyloid deposition in the brain. (revised per Amendment 04) This criterion will confirm amyloid pathology and allow for the inclusion only of subjects with MCI due to AD/Mild AD. Use of a historical amyloid positive PET (conducted within 12 months before the planned randomization date) is acceptable for determination of eligibility (providing that the historical imaging data is made available to the sponsor), but will not suffice for baseline assessment if the subject wishes to consent to the amyloid PET longitudinal substudy. Historical CSF samples

may be analyzed to confirm amyloid pathology, if collected, processed, and stored under appropriate conditions and approved by the sponsor. (revised per Amendments 04 and 06)

Subjects who consent to participate in the amyloid and tau-PET longitudinal substudies will have assessments at 12 months (amyloid PET only), 24 months (all applicable substudy assessments), or at the ED Visit in the Core Study and at 24 months or at the ED Visit in the Extension Phase. (revised per Amendments 04, 05, and 06)

Subjects who consent to the CSF substudy will have samples taken at 24 months or at the ED Visit in both the Core Study and Extension Phase for PD and biomarker assessments. (revised per Amendment 06)

Safety Assessments (both Core Study and Extension Phase)

Safety will be assessed by monitoring and recording all AEs and serious adverse events (SAEs); regular monitoring of hematology, blood chemistry, and urinalysis; periodic measurement of vital signs; ECG recordings (evaluated by a central reader in the Core Study); physical, dermatologic, and neurologic examinations; assessment of suicidality, events of possible signals of drug abuse potential, and MRIs during the Treatment Period. (revised per Amendments 01 and 06)

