9.5.1.5.6 ELECTROCARDIOGRAMS

Electrocardiograms will be obtained as designated in [Table 4](#) and [Table 5](#). A single 12-lead ECG will be recorded after subjects have been resting in the supine position for at least 5 minutes. If the QTcF machine read is greater than 440 ms on the first single 12-lead ECG, 2 additional 12-lead ECGs will be performed 1 minute apart and the mean of the 3 QTcF values will be calculated. All ECG recordings will be evaluated by a central reader. (revised per Amendments 01 and 06)

On any study day when ECG, vital signs, and blood samples are taken, it is recommended that these procedures should be conducted in the following order: ECG first, followed by vital signs, and then blood samples.

An ECG abnormality may meet the criteria of an AE as described in this protocol (see [Section 9.5.1.5.1](#)) and the CRF Completion Guidelines. In these instances, the AE corresponding to the ECG abnormality will be recorded on the AEs eCRF.

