Subjects who complete the 24 months of Extension Phase treatment, or discontinue the study drug are required to complete the Follow-up Visit, 1 month after their last dose. The study will end when the last subject has completed the last Extension Phase study visit.

Treatment

Elenbecestat will be supplied by the sponsor as tablets of 50-mg dose strength in bottles of 35 tablets. Each subject will receive 1 tablet of 50 mg elenbecestat, to be administered orally QD in the morning with or without food.

Assessments

Assessments will be conducted as shown in [Table 5](#) Visit 15 (Day 1 of the Extension Phase) and as shown in [Table 9](#), for all other Extension Phase visits following the guidelines as indicated for the Core Study in [Section 9.5](#). Concomitant therapy is allowed as stated in [Section 9.4.7](#) and treatment compliance and accountability will be performed as indicated in [Section 9.4.8](#), and [Section 9.4.9](#), respectively.

Safety assessments (physical examinations, neurological examinations, vital signs, safety laboratory tests, ECGs [no central reading of ECGs], signals of potential abuse, pregnancy test for females of child-bearing potential, Columbia Suicide Severity Rating Scale (C-SSRS), and assessment of suicidal thinking/behavior, immunological assessments, safety magnetic resonance imaging (MRI) will be monitored according to [Table 9](#) and all adverse events (AEs) and serious adverse events (SAEs) recorded.

A full neurologic examination will be performed at the start of the Extension Phase (during Visit 15, the last visit of the Core Study), and at Visit 24/ED, but will be abbreviated for all other timepoints.

Safety laboratory blood tests will be collected as indicated in [Table 9](#) and analyzed by a central laboratory.

Blood samples for pharmacodynamic (PD) and biomarker analyses ([Table 7](#)) will be collected as indicated in [Table 9](#). The blood sample for PD analyses should be collected at fasting or at least 2 hours after the most recent meal.

Subjects that have consented to the optional CSF substudy (either at the start of the Core Study or Extension Phase) will have samples taken as indicated in the Table of Assessments to analyze PD and biomarkers ([Table 7](#)). Longitudinal CSF sample is taken before other Visit 24 assessments and whilst subject is still on study drug; for ED, CSF should be taken and no longer than 7 days after the last dose.

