Safety analysis will be performed similarly to analyses in the Core Study. The Core Study baseline will be used for subjects who are randomized to elenbecestat initially, the Extension Phase baseline will be used for subjects who are randomized to placebo but receive elenbecestat during the Extension Phase. The incidence of AEs (including changes from baseline in physical and neurological examinations, and dermatological assessments), out-of-normal-range laboratory safety test variables, abnormal ECG findings, out-of-range vital signs, suicidality (C-SSRS), and changes from baseline in laboratory safety test variables, ECGs, safety MRI, vital sign measurements will be summarized by using descriptive statistics.

Efficacy Analyses

The following efficacy endpoints will be summarized by descriptive statistics and graphs:

- Changes from baseline in CDR-SB, ADCOMS, MMSE, FAQ, ADAS-cog14, and ADAS-cog14 Word List (immediate recall and delayed recall)
- Time to conversion to dementia for subjects who were not clinically staged as dementia at Core Study baseline based on clinical diagnosis
- Change from baseline in NPI-10 and NPI-12
- Proportion of subjects who receive increase and/or initiation of other AD pharmacotherapies

A delayed-start analysis ([Liu-Seifert et al., 2015](#)) will be performed for each efficacy endpoint at various scheduled visits in the Extension Phase. In addition, a mixed effects model for repeated measures (MMRM) will be used to analyze the above endpoints where appropriate.

Biomarker Analyses

The following biomarker endpoints will be summarized by descriptive statistics and graphs:

- Change from baseline in amyloid PET standardized uptake value ratio (SUVR)
- Change from baseline in tau PET signal
- Change from baseline in total hippocampal volume as measured by vMRI
- Change from baseline in the preservation of connectivity as measured by fMRI
- Change from baseline in t-tau, p-tau, A β (1-42) and A β (1-x) in CSF
- Change from baseline A β (1-x) in plasma
- Change from baseline in exploratory biomarkers eg, NFL, VILIP1, YKL-40, and Ng in CSF and plasma

A delayed-start analysis and MMRM model will be used to analyze these biomarker endpoints.

The relationship between efficacy endpoints and biomarker endpoints will be explored using correlation analysis.

Sample Size Rationale

Not applicable.

Table 9 Schedule of Procedures/Assessments in Extension Phase

Phase	Extension											

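### Extension ECG change compares centrally read Core baselines with ECGs that are not centrally read, so the open-label QTcF change may be biased downward by an unknown amount

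*Protocol*

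**What the plan says.** **Core reading method.** Section 9.5.1.5.6 states: "All ECG recordings will be evaluated by a central reader". The synopsis (Safety Assessments) limits this to the Core: "ECG recordings (evaluated by a central reader in the Core Study".

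**Extension reading method.** The synopsis description of the Extension lists "safety blood and urine laboratory tests, ECGs [no central reading of ECGs], suicidality, neurological examination, NPI, and signals of abuse potential". Appendix 5 (Assessments) repeats the exclusion: "ECGs [no central reading of ECGs], signals of potential abuse". Table 9 note f bases the repeat-ECG rule on the machine value.

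**Baseline for change.** Appendix 5 (Safety Analyses) summarizes changes from baseline in ECGs. For one group, "The Core Study baseline will be used for subjects who are randomized to elenbecestat initially"; for the other, "the Extension Phase baseline will be used for subjects who are randomized to placebo but receive elenbecestat during the Extension Phase". Section 9.1 and Appendix 5 place the Extension baseline at Visit 15, the last Core visit.

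**Role of ECG.** Appendix 5 makes long-term safety and tolerability the primary objective and names ECG in the primary endpoint.

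**Machine versus central reads.** In the revision history, the Amendment 06 rationale for exclusion criterion 14 says: "Machine read QTcF values might be lower than central reads". This explains a trigger that is still in the current text, so it is not superseded material.

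**The concern.** A change score is interpretable only if both values come from the same measurement process. Here the baseline falls under one reading rule and every follow-up value falls outside it. Any systematic difference between the two reads is then counted as change on treatment.

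The sponsor's own remark points one way. If machine values are lower, a QTcF rise in the Extension would look smaller than it is. Everyone in the Extension takes elenbecestat, so no concurrent control would reveal the shift. For subjects who took placebo in the Core, the step from Visit 15 into the Extension is their only on-drug ECG change.

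**Working it through.** There is no figure of the plan to reproduce: Appendix 5 gives the Extension sample size as not applicable, and no reader difference is stated anywhere.

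**Step 1. Which read applies where**

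| Value | Visit | Reading rule |
|---|---|---|
| Baseline, first on elenbecestat | Visit 2 (Table 5) | Core: central |
| Baseline, placebo switchers | Visit 15 (Table 5; note e requires the ECG if the subject continues) | Core: central, subject to confirmation |
| Follow-up, both groups | Visit 17 onward (Table 9) | Extension: not central |

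The status of Visit 15 needs confirming. Figure 1 note b and Appendix 5 also treat it as Day 1 of the Extension.

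**Step 2. Effect on the mean change**

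Let C be the central read, M = C − b the non-central read, and Δ the true change, C(follow-up) − C(baseline).

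- As written: M(follow-up) − C(baseline) = Δ − b.
- Same method at both visits: M(follow-up) − M(baseline) = Δ.
- Core, by arm: central minus central, so b does not enter.

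If Visit 15 turned out to be read non-centrally, the switchers' change would be Δ. The group first on elenbecestat would still show Δ − b, and the two Extension groups would then differ by b through reading method alone.

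**Step 3. Do the triplicate rules offset this?**

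Table 5 note i calls for two more ECGs when the machine QTcF exceeds 440 ms; Table 9 note f does so above 450 ms. A simulation with no drug effect applied 440 ms at baseline and 450 ms at follow-up, with 1,000,000 subjects per setting. All distributional inputs are assumptions. The QTcF exclusion at screening was not applied.

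| Mean / between-subject SD / within-subject SD (ms) | b = 0 | b = 2 | b = 5 | b = 10 |
|---|---|---|---|---|
| 410 / 18 / 8 | +0.14 | −1.86 | −4.87 | −9.93 |
| 420 / 18 / 8 | +0.25 | −1.76 | −4.79 | −9.84 |
| 420 / 20 / 12 | +0.40 | −1.61 | −4.60 | −9.65 |

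Entries are the mean change in ms when the true change is zero. The unequal triggers alone add between 0.07 and 0.40 ms. With the same trigger and the same reading method the mean is zero within simulation error (−0.02 to +0.03 ms). The offset is therefore small, and the net shift is downward once b exceeds roughly 0.5 ms.

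**Step 4. Threshold counts**

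At b = 5 ms, the share above 450 ms is 0.6% to 3.7% on machine reads and 1.9% to 8.1% on central reads of the same recordings. These shares depend on the assumed distributions. Only the follow-up value enters them, so a different baseline does not change them.

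**The case against.** **The direction is not established.** This stands. The sponsor says machine values might be lower and gives no measurement. Moreover, the absence of central reading does not mean the analysed value is an unedited machine read. If it is a local over-read, the documents give no direction. What is fixed by the text is that the reading rules differ.

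**Appendix 5 names the baseline visit, not the read.** True: a like-for-like machine comparison would be compatible with the wording, since machine QTcF exists at Core visits for the triplicate rule. But the read required of Core ECGs is the central one, and nothing shown calls for a machine-read baseline, so mixing methods is the default. The protocol itself sets both the reading rule and the baseline; this is a mismatch, not a detail left open.

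**The consequence is limited.** This stands in large part. The Extension summary is descriptive. The Core supplies 24 months of placebo-controlled, centrally read ECGs at the same 50 mg dose. Section 7.1 reports that an effect above 10 ms was excluded for single doses up to 200 mg, four times the trial dose.

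**Stronger inferences a reader might draw.** One is that the Extension understates QTcF change by 2 to 10 ms. The gap between the 440 ms machine trigger and the 450 ms central limit is a screening margin, not a measured difference. Another is that the shift could hide an effect like the 14.9 ms seen at 800 mg. Even b = 10 ms would leave 14.9 − 10 = 4.9 ms visible, and 800 mg is sixteen times the trial dose. The documents support neither.

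**Conclusion.** The point holds as a mismatch of reading methods with a conditional direction. On the current text, Extension ECG change sets a non-central follow-up against a centrally read Core baseline: certainly at Visit 2, and at Visit 15 if the Core rule governs that visit. Any systematic reader difference passes one for one into the mean change, and the Extension has no control group to expose it. If the sponsor's remark is right and the analysed values are machine reads, the bias is downward. Its size cannot be derived from the documents, and the simulated figures rest on assumed values of b and of the QTcF distribution.

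Placebo switchers are the most exposed. Subjects first on elenbecestat also have centrally read on-drug ECGs from the Core, and the Core treatment comparison is intact. This is a worthwhile, inexpensive improvement to the Extension safety summary, not a threat to the trial's main QT evidence.

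**What to change.** State in Appendix 5 (Safety Analyses) that Extension ECG change is computed from a baseline read by the same method as the follow-up, namely the machine or site-read QTcF of the same Visit 2 or Visit 15 tracing. Report centrally read Core ECG results separately. Where no same-method baseline can be retrieved, do not present the cross-method change as a drug effect. Confirm which reading rule applies to the Visit 15 ECG.

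Label absolute threshold counts in the Extension as non-central reads, because the new baseline does not correct them. Table 5 note i and Table 9 note f give different triplicate triggers and should be reconciled; no value is proposed here.

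**Cost.** No new ECGs and no additional reader. Machine values for two Core visits must be entered for subjects who continue, across approximately 250 sites in this study. The protocol does not say whether the machine value is already captured on the eCRF, although Section 11.3 lists ECGs among the source documents. Entering both visits for every continuing subject avoids signalling the original allocation. The statistical price is noisier values than central reads would give.

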ADAS-cog = Alzheimer’s Disease Assessment Scale - cognitive subscale, AE = adverse event, CBP = child-bearing potential, CDR = Clinical Dementia Rating, CSF = cerebrospinal fluid, C-SSRS = Columbia Suicide Severity Rating Scale, ED = Early Discontinuation, FAQ = Functional Assessment Questionnaire, MMSE = Mini Mental State Examination, MRI = magnetic resonance imaging, NPI = Neuropsychiatric Inventory, PD = pharmacodynamic, PET = positron emission tomography, QTcF = QTc interval calculated using Fridericia’s formula, UNS = Unscheduled Visit

- a: A window of ±3 days will be permitted for Visits 16 and 17. A window of ±7 days will be permitted for Visits 18 and 19. A window of ±10 days will be permitted for Visit 20 to 24 inclusive. These windows should be calculated from Extension Phase Day 1. A window of ±3 days will be permitted for the Follow-up Visit calculated from the last Extension Phase dose.
- b: Subjects who permanently discontinue taking study drug before end of treatment will undergo an ED Visit within 7 days of their last dose of study drug. In addition, a Follow-Up Visit will be scheduled 4 weeks after the last dose of study drug.
- c: Unscheduled visits may be conducted at any time that additional assessments, including MRI scans, are clinically indicated in the judgment of the investigator.
- d: Measurements of body temperature and sitting blood pressure and sitting heart rate will be obtained.
- e: A full neurologic examination will be performed at Visit 24 (or ED). Neurologic examinations at the other visits will focus on new symptoms and signs.
- f: Single 12-lead standard ECGs will be recorded. If the QTc interval calculated using Fridericia’s formula (QTcF) machine read is greater than 450 ms, perform 2 more 12-lead standard ECGs 1 minute apart and take the mean of the 3 QTcF values.
- g: If dipstick urinalysis performed at site is abnormal, a urine sample will be sent to the central laboratory for full urinalysis

Table 9 Schedule of Procedures/Assessments in Extension Phase

Phase	Extension										
Period	Treatment ^a									1 Month Follow-Up	UNS ^c
Day in Extension Phase	15	29	57	120	245	365	484	610	729	ED ^b	
Visit	16	17	18	19	20	21	22	23	24		
Weeks elapsed since 1st dose in Extension Phase	2	4	8	17	35	52	69	87	104		
Nominal months elapsed since 1st dose in Extension Phase	0.5	1	2	4	8	12	16	20	24		
Procedures/Assessments											

- h: More frequent testing may be required per local regulations. If urine dipstick pregnancy test is positive, a blood sample will be drawn for serum pregnancy testing by the central laboratory.
- i: The subject components of these assessments are to be completed in the morning whenever possible, or consistently at the same time of day. Ideally, the subject component of these assessments should be completed before more invasive assessments or procedures (eg, physical examination, ECG, blood draws).
- j: PD and biomarker blood samples should be collected at fasting or at least 2 hours after the most recent meal and, as far as is feasible, samples should be taken at the same time of day at all visits. Samples should be taken predose.
- k: For subjects who consent to participate in the CSF longitudinal substudy. Visit 24 (or ED) also includes blood PD assessments and so the subject will be dosed at the clinic on these days. A CSF sample will be collected by lumbar puncture (LP) between 4 and 8 hours postdose and at the same time of day as the subject's Screening LP (±1 hour). The CSF sample will be taken with the subject fasting (preferred) or at least 2 hours after the most recent meal. A gravity drip collection method must be used. If performed on the same day as the cognitive tests, the LP will be performed after the cognitive tests; the subject should rest and drink some fluid to hydrate after the cognitive tests and before the LP. Subjects will be encouraged to stay at the site after completion of LP for medical observation. The CSF sample will not be taken at the ED Visit if this visit occurs within 39 weeks of treatment or 3 months of a previous CSF sample. If at an ED Visit, the subject has already stopped study drug, then no dosing will take place, but the CSF sample will still be collected unless it was already collected within the past 3 months. Subjects receiving concomitant anticoagulation/antiplatelet therapy should have prothrombin time and International Normalized Ratio (INR) (derived from prothrombin time) before LP; if they are assessed by the investigator to be at risk for bleeding, they are to be excluded from CSF collection. Note that subjects who are assessed by both amyloid PET and CSF are required to wait for a minimum of 48 hours between the 2 procedures.
